8.2.5 Parameter Estimates for Primary Endpoints

8.2.5.1 Assumptions for the Effect of MK-8931

Extrapolations out to 24 months (Week 104) were performed on the 18-month (Week 78) parameter assumptions used in the initial 78-week trial and these extrapolations are presented below in [Table 6](#).

Table 6 Parameter Assumptions for Progression Rate on Placebo, Standard Deviations, and Within Endpoint Correlations for ADAS-Cog, ADCS-ADL, and CDR-SB

Endpoint	104-Week Placebo/ MK-8931 40 mg Progression Rate	Baseline Standard Deviation	104-Week Standard Deviation	Correlation (Baseline, Week 104)
ADAS-Cog	7.45	7.75	14.97	0.65
ADCS-ADL	-11.73	10.71	20.21	0.61
CDR-SB	2.91	2.28	4.65	0.56

ADAS-Cog=Alzheimer's Disease Assessment Scale Cognitive subscale; ADCS-ADL=Alzheimer's Disease Cooperative Study Activities of Daily Living Inventory; CDR-SB=Clinical Dementia Rating Sum of Boxes

8.2.5.2 Power Calculations

Power calculations for the change-from-baseline treatment difference at 24 months (Week 104) were performed (via simulation) for ADAS-Cog and ADCS-ADL, even though there are no formal hypotheses for these endpoints in the long term safety trial. As shown in [Table 7](#) both of these hypotheses are underpowered at Week 104, both marginally and when applying an informal sequential testing approach. Specifically, it is possible that formal statistical significance may be observed in the initial 78 week trial (under the prespecified multiplicity approach), while nominal marginal significance (ie, p-value < 0.02495) fails to be observed at Week 104, even if the true underlying effect of MK-8931 continues to increase. This is due to the assumed increased variance and dropout rate over time, with 90% of subjects who complete the base study assumed to continue on into the extension.

Table 7 Power Calculations (MK-8931 40 mg / MK-8931 40 mg vs. Placebo / MK-8931 40 mg)

Marginal Probability [†]	(%)
ADAS-Cog at Week 104	62.3
ADCS-ADL at Week 104	74.1
ADAS-Cog and ADCS-ADL at Week 104	48.0
Sequential Probability	
Success [‡] for ADAS-Cog and ADCS-ADL at Week 78 and ADAS-Cog at Week 104	58.0
Success [‡] for ADAS-Cog and ADCS-ADL at Week 78 and ADCS-ADL at Week 104	66.5
Success [‡] for ADAS-Cog and ADCS-ADL at Week 78 and ADAS-Cog and ADCS-ADL at Week 104	46.1
Conditional Probability	
Success [‡] for ADAS-Cog at Week 104 given success on ADAS-Cog and ADCS-ADL at Week 78	68.4
Success [‡] for ADCS-ADL at Week 104 given success on ADAS-Cog and ADCS-ADL at Week 78	78.4
Success [‡] for ADAS-Cog and ADCS-ADL at Week 104 given success on ADAS-Cog and ADCS-ADL at Week 78	54.4
[†] Marginal power calculations at Week 104 do not require success at Week 78. [‡] 40 mg dose only Calculations are based on N=1710 randomized (570 subjects/arm) incorporating the assumed dropout rate of 30% at Week 78 and 45% at Week 104. (α = 0.0249).	

8.2.6 Dropping Dose Arms

In the event of a dose being dropped, all subjects will receive the remaining active dose.

8.2.7 Accounting for Missing Data

Common reasons for discontinuation from the trial may include lack of efficacy, clinical or laboratory adverse experiences, relocation, withdrawal of consent, protocol violations, and/or data processing issues. Missing data caused by relocation and data processing issues are likely to be missing-completely-at-random (MCAR). On the other hand, missing data caused by discontinuation due to lack of efficacy may be missing-at-random (MAR) because the discontinuation may depend on the observed efficacy outcomes. The MAR or missing-not-at-random (MNAR) mechanisms might each underlie the other reasons to some extent. If treatment in large part determines the loss of data for these other reasons (such as clinical or laboratory adverse experiences), the mechanism may be close to MAR because treatment assignment is an observed variable and included in the analysis model. Based on prior trial results, missing data due to other reasons is relatively infrequent.

No explicit imputation of missing data (beyond the limited imputation performed within an assessment) will be done for the primary analysis approach.

A pattern-mixture model based on the tipping-point approach will be used to assess the robustness of the primary analysis approach. For a given constant, c , the tipping point analysis is conducted in a fashion similar to that used in standard multiple imputation^(25,26,27), whereby m complete datasets are randomly generated using the original observed dataset. These m complete datasets are subsequently analyzed using the primary model, and the results of those analyses are then combined. The construction and analysis of these m ($=50$) datasets requires four primary steps:

- 1) Using a Markov Chain Monte Carlo method⁽²⁸⁾, make the observed dataset monotone-missing. This will be accomplished for each treatment group using “proc mi” within SAS 9.3 by utilizing the options “mcmc chain=multiple impute=monotone;”, in conjunction with all of the covariates (excluding treatment) included in the primary analysis model. The random seed will be set equal to 8931017. This step will generate m monotone-missing datasets.
- 2) Applying parametric regression to the monotone-missing datasets, impute the missing values in a stepwise fashion starting with the first postdose timepoint. This will be accomplished for each treatment group using “proc mi” within SAS 9.3 utilizing the option “monotone reg”, in conjunction with all of the covariates (excluding treatment) included in the primary analysis model. The random seed will be set equal to 8931017. This step will generate m complete datasets.
- 3) To implement the tipping-point aspect of the procedure, subtract a constant c from each of the imputed values of the active arms (to the detriment of active).

- 4) Analyze each of the post-imputation complete datasets using the primary model, obtaining point estimates for the mean of interest (eg, change-from-baseline treatment difference at 104 weeks) and the associated variance.

Using “proc mianalyze” within SAS 9.3, the $m=50$ means and variances from the m analyses will be combined to obtain the final test statistic and p-value⁽²⁵⁾. The final test statistic $\bar{Q} / (T^{(1/2)})$ is approximately distributed as t_v , where \bar{Q} is the sample mean of the m mean estimates, $T = \bar{U} + (m+1) (B/m)$, \bar{U} is the sample mean of the m variance estimates, and B is the sample variance of the m mean estimates. The degrees of freedom, v , will be computed as follows⁽²⁹⁾, $v = [(v_1)^{-1} + (v_2)^{-1}]^{-1}$, where $v_1 = (m-1) [1 + (\bar{U}/(1+m^{-1}) B)]^2$ and $v_2 = (1-\gamma) v_0 (v_0 + 1) / (v_0 + 3)$, with $\gamma = (1+m^{-1}) B / T$ and where v_0 represents the complete-data degrees of freedom .

This procedure will be repeated (using the same m imputed datasets) until the smallest c is found such that the significant result turns non-significant (ie, $p \geq 0.02495$). This tipping point value c provides a measure of robustness of the primary result. A relatively large value of c implies better robustness of the primary analysis against the impact of missing data in the study. It is noted that when $c=0$ the tipping point analysis described above corresponds to an analysis conducted under the assumption that the missing data are MAR. For values of c larger than 0, the tipping point analyses do not assume that the missing values follow a MAR mechanism. In fact, the analysis is based on a special MNAR mechanism in which all missing data in the active arm are assumed to have a worse response by a constant amount of c than the values would have had under MAR, while the missing data in the control group are assumed to be the same as that obtained under MAR.

It may be necessary to adjust c , in order to calibrate between the two analysis approaches (ANCOVA vs. MI), should a value of $c=0$ yield a different p-value than is produced from the primary ANCOVA analysis model. This will be accomplished by subtracting the calibration value C_{prim} from c , where C_{prim} is the offset to be applied to the active arm, per the above MI approach, that will yield the same p-value as produced by the primary ANCOVA analysis.

Handling of Missing Items Within a Clinical Assessment

The final scores of the ADAS-Cog, ADCS-ADL, NPI, MMSE, and CDR-SB are all constructed from multiple subquestions within each assessment. It is possible that one or more subquestions may be missing within each assessment. In this event, the last recorded score for this subquestion(s) may be carried forward from the most recent postdose visit (Last Observation Carried Forward approach). In a similar fashion, missing baseline values may be carried over from the most recent screening visit, if available. Baseline/screening values will never be carried forward to impute missing postdose values. Due to the degenerative properties of AD, with subjects expected to worsen over time, an individual subquestion will not be carried forward for more than one visit. If the same subquestion is missing two visits in a row, then LOCF will be applied to the first missing visit and the subquestion will remain as missing for the second visit (with the total score to then be computed as missing). Further, the total score will be computed as missing if too many

subquestions, prior to applying the LOCF approach, are missing (see endpoint-specific details below). This single imputation approach allows the total score to be calculated using the strength of the other subquestions collected at that time, for that subject. The Sponsor believes this approach to be more accurate than either setting the entire score to missing or to imputing the worst possible score. More complicated missing data approaches are not thought to be warranted, since the amount of missing data within an assessment is expected to be extremely low.

For Baseline ADCS-ADL only (from the initial 78-week trial): Past experience indicates that some subquestions on the ADCS-ADL may mistakenly be omitted at the time of administration. Should this occur at baseline, there will be no opportunity to employ the stated LOCF approach. To avoid a missing total score on the ADCS-ADL (and the subsequent removal of the subject from the primary ADCS-ADL population), the worst possible score for that subquestion will be imputed. Note that this imputation approach will only be implemented for ADCS-ADL (given the relatively small impact of the individual subquestions on the overall score) and only at baseline. A total score will only be computed if the number of missing subtotals is strictly less than three.

Endpoint specific details are as follows:

ADAS-Cog and MMSE: The site will be instructed to enter the worst possible score if the subject is unwilling or unable to answer a subquestion due to reasons related to the area the subquestion is trying to address. If the subject is unable to answer a subquestion for some other reason, then the site will be instructed to leave the subquestion as missing. For both the ADAS-Cog and the MMSE, a total score will be calculated if the original number (prior to applying LOCF) of missing subtotals is strictly less than three.

CDR-SB, ADCS-ADL, and NPI: The CDR-SB, ADCS-ADL, and NPI are all administered to the caregiver, not the subject, so no within-assessment missing data are expected (though missing subquestion data is still possible due to data entry error or errors in test administration). For ADCS-ADL and NPI, a total score will be calculated if the original number of missing subtotals is strictly less than three. For CDR-SB, a total score will be calculated if the original number of missing subtotals is strictly less than two.

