8.2 Efficacy Analyses

Details pertaining to the analysis of all endpoints are discussed below. **Table 5** provides a summary of the Primary Endpoints to be analyzed, as well as the analysis approaches that will be used.

The primary analysis approach will include all efficacy observations in the FAS population, including those obtained after the discontinuation of study medication.

Table 5 Analysis Strategy for Primary Endpoints

Endpoint/Variable (Description, Time Point)	Primary vs. Supportive Approach	Statistical Method [†]	Analysis Population	Missing Data Approach
Primary Endpoints				
Primary Endpoints:				
CFB at Week 104 (Visit 13) in ADAS-Cog score	P	Longitudinal ANCOVA	FAS	Model-based
	S	Longitudinal ANCOVA	FAS	Pattern-Mixture Model (Tipping Point)
	S	Longitudinal ANCOVA (Exclude data collected after the introduction of AChEIs and/or study medication discontinuation)	FAS	Model-based
	S	cLDA	MFAS	Model-Based
CFB at Week 104 (Visit 13) in ADCS-ADL score	P	Longitudinal ANCOVA	FAS	Model-based
	S	Longitudinal ANCOVA	FAS	Pattern-Mixture Model (Tipping Point)
	S	Longitudinal ANCOVA (Exclude data collected after the introduction of AChEIs and/or study medication discontinuation)	FAS	Model-based
	S	cLDA	MFAS	Model-Based

The primary model contains categorical terms for treatment, time, geographic region, gender, APOE genotype, study cohort (from initial 78-week trial), and the interaction of time-by-treatment, with the Baseline values of MMSE, and age included as continuous covariates. Terms for the baseline value and the baseline-by-time interaction of the dependent variable will also be included.
 
ADAS-Cog=Alzheimer’s Disease Assessment Scale Cognitive subscale; ADCS-ADL=Alzheimer’s Disease Cooperative Study Activities of Daily Living Inventory; CDR-SB=Clinical Dementia Rating Sum of Boxes; CFB=Change from Baseline; ANCOVA=Analysis of Covariance; cLDA=Constrained Longitudinal Data Analysis; FAS=Full Analysis Set; MMSE=Mini-Mental State Examination; NA=Not Applicable; NPI=Neuropsychiatric Inventory; P=Primary; S=Supportive.
				

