Three supportive analyses will be conducted on each of the Coprimary Endpoints. These analyses will be conducted to assess the effect of 1) missing data using a pattern-mixture model (“tipping-point” analysis), 2) the use of off-regimen data after the subject has permanently discontinued trial medication or after the subject has initiated AChEIs and 3) analyzing the data using the cLDA model on the MFAS population.

For the first sensitivity analyses (tipping-point), the model-based estimates of the mean treatment difference on the change scores, along with the corresponding confidence intervals and p-values will be provided for a range of c values which have been subtracted from the values imputed for the active arms (see 8.2.10) for more details). Of specific interest is the smallest c value that, for a given endpoint, transforms a statistically significant result to a non-statistically significant result.

For the second sensitivity analysis (excluding observations obtained after study medication discontinuation or after the initiation of AChEIs, memantine, or Vitamin E), the model-based estimates of the mean treatment difference on the change scores, along with the corresponding confidence intervals and p-values will be provided.

For the third sensitivity analysis (cLDA model on the MFAS population), the analysis of the primary efficacy endpoints will be conducted using a constrained longitudinal data analysis (cLDA) method proposed by Liang and Zeger [11]. This model assumes a common mean across treatment groups at baseline and a different mean for each treatment at each of the post-baseline time points. The response vector consists of baseline and the values observed at each post-baseline time point. Additional details pertaining to the cLDA model are included in Section 12.5. The model-based estimates of the mean treatment difference on the change scores, along with the corresponding confidence intervals and p-values will be provided as obtained using the cLDA model, with all of the same covariates that were included in the primary model (now excluding the terms for baseline and baseline-by-time interaction). An unstructured covariance model will be used.

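### The tipping-point analysis subtracts c for both primary endpoints, which on ADAS-Cog favours MK-8931, so a significant ADAS-Cog result can never tip

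*Combined protocol and SAP*

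**What the plan says.** Table 5 (Section 8.2) lists a pattern-mixture tipping-point analysis as supportive for Week 104 change in both ADAS-Cog and ADCS-ADL. Section 8.2.7 sets out the procedure: impute with m = 50, shift the imputed values in the active arms, analyse with the primary model, pool, and repeat until the smallest c is found that gives p of at least 0.02495.

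The shift itself is step 3: "subtract a constant c from each of the imputed values of the active arms (to the detriment of active". Section 8.2.1 describes the same operation, with results to be shown "for a range of c values which have been subtracted from the values imputed for the active arms". Neither place gives a different sign for either endpoint.

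The purpose is stated just after the steps: "all missing data in the active arm are assumed to have a worse response by a constant amount of c". The text covers c = 0, which it equates with missing at random, and then positive c: "For values of c larger than 0, the tipping point analyses do not assume that the missing values follow a MAR mechanism". Negative c is not mentioned. A larger tipping value is to be read as greater robustness.

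**The concern.** On a scale where a rise is deterioration, subtracting a positive number from imputed scores makes those patients look better. If ADAS-Cog is such a scale, the written rule turns a stress test into a bonus for MK-8931, and the search for the smallest c that removes significance has no end point.

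This is the only analysis in Table 5 that departs from missing at random; the other supportive rows are model-based. Table 7 assumes 45% dropout by Week 104, so nearly half the Week 104 values would be imputed and shifted. One of the two primary endpoints would have no working check on that assumption, and a fragile ADAS-Cog result could pass as one that no c overturns.

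**Working it through.** **1. Direction of each scale.** Section 8.2.7 states that patients are expected to deteriorate over time. The Table 6 column "104-Week Placebo/ MK-8931 40 mg Progression Rate" gives +7.45 for ADAS-Cog and -11.73 for ADCS-ADL. So a higher ADAS-Cog is worse and a lower ADCS-ADL is worse. Section 8.2.1 defines the treatment difference as MK-8931 minus placebo, so benefit is negative on ADAS-Cog and positive on ADCS-ADL.

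**2. Size of the shift.** If a fraction f of active-arm values is imputed and each is reduced by c, the active mean, and hence the difference, moves by -f × c. With f = 0.45 this is -0.45c. On ADCS-ADL the movement is against MK-8931, as intended. On ADAS-Cog it is in its favour.

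**3. Could the extra variance from the shift remove significance?** No. For large c:
- the difference tends to -f × c;
- the shift adds variance f(1 - f)c² within the active arm, half of that to the pooled residual variance, and so f(1 - f)c²/n to the variance of the difference;
- |t| therefore tends to √(n × f/(1 - f)) = √(570 × 0.45/0.55) = 21.6.

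The critical value is about 2.24 (two-sided 0.02495). Starting from a significant benefit, |t| rises with c, and any later fall is only towards 21.6.

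**4. Plan's own figures.** The documents state no tipping value and no Week 104 treatment effect, so the Table 7 power cannot be reproduced independently. It can be solved backwards.
- Residual SD = SD × √(1 - r²): ADAS-Cog 14.97 × √(1 - 0.65²) = 11.38; ADCS-ADL 20.21 × √(1 - 0.61²) = 16.01.
- Observed n per arm = 570 × 0.55 = 313.5, with two-sided alpha 0.0249.
- Effect = (z for alpha + z for power) × residual SD × √(2/n). Power of 62.3% gives 2.32 ADAS-Cog points (31.2% of 7.45). Power of 74.1% gives 3.70 ADCS-ADL points (31.5% of 11.73).

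A single slowing of 31.5% gives power of 63.3% and 74.1%, so the inputs are coherent.

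**5. Simulation.** Inputs: 570 per arm, Table 6 SDs and correlations, 45% missing completely at random, assumed slowing 31.2%, regression imputation by arm with m = 50, ANCOVA, and pooling with the degrees of freedom in the plan. One example dataset per endpoint was taken with a primary p between 0.004 and 0.012, because the tipping search matters only after a significant result.

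| c | ADAS-Cog, c subtracted (as written) | ADAS-Cog, c added | ADCS-ADL, c subtracted (as written) |
|---|---|---|---|
| 0 | -2.38, p = 0.006 | -2.38, p = 0.006 | 3.35, p = 0.0093 |
| 1 | -2.83, p = 0.0011 | -1.93, p = 0.026 | 2.91, p = 0.024 |
| 1.5 | -3.05, p = 0.00045 | -1.70, p = 0.049 | 2.68, p = 0.037 |
| 2 | -3.28, p = 0.00017 | -1.48, p = 0.087 | 2.46, p = 0.055 |
| 5 | -4.63, p < 0.0001 | -0.12, p = 0.89 | 1.12, p = 0.38 |

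At c = 100 the written rule gives t = -21.1 on ADAS-Cog, close to the limit in step 3. With c added, this ADAS-Cog result tips at about 1 point. The ADCS-ADL rule works as written and tips between 1 and 1.5 points.

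**6. Repetition.** Of 150 simulated ADAS-Cog datasets, 98 were significant in favour of MK-8931 at c = 0. Subtracting c tipped 0 of 98 over a grid from 0.25 to 200. Adding c tipped all 98, with median c 1.7 (interquartile range 0.9 to 3.0).

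**The case against.** The strongest reply is that the intended direction is not in doubt. Step 3 itself says the shift should hurt the active arms, the later paragraph says missing active data are taken to be worse, and the amendment's rationale describes c as a detrimental effect. A programmer who follows the purpose would add c on ADAS-Cog. Nor does any sentence formally require c to be positive. The printed estimates across c would also show MK-8931 improving under a supposed penalty, which should prompt a correction.

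Beyond that, the analysis is supportive, the trial has no formal hypotheses, the comparison is acknowledged to be underpowered, and the primary model is untouched. The claim that the result cannot tip needs a result that is already significant in favour of MK-8931 under imputation at c = 0. The tipping values also depend on an assumed effect and a simplified simulation.

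Most of this is fair as to importance. It does not remove the error. The clear intent shows that the written operation is wrong for ADAS-Cog, and reversing the sign silently would be an undocumented departure from a plan precise enough to fix SAS options and a random seed. Negative c would fit neither a search for the smallest c nor the reading of a large c as reassurance. The condition on significance is the normal setting in which the search is run.

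**Conclusion.** The plan is wrong as written on this point. For ADAS-Cog the prescribed operation contradicts its stated purpose, and nothing in the document reverses the sign, rescores the scale or provides for negative c. For a positive c and an ADAS-Cog result that is significant in favour of MK-8931 at c = 0, the literal rule moves the difference by about 0.45c the wrong way and never reaches a tipping point. Relative to the intended penalty, the discrepancy is about 2 × 0.45 × c = 0.9c points.

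The direction depends only on Table 6 and the wording of the rule. The shift per point of c depends on the 45% missing fraction. The tipping values of 1 to 3 points rest on the back-solved effect, missingness completely at random and a model with only baseline and Week 104, and should be read as illustrations. The primary longitudinal ANCOVA and the ADCS-ADL tipping-point analysis are not affected. Because Section 8.0 says that no separate SAP will be issued, no later analysis plan is due to put this right.

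**What to change.** In Section 8.2.7 step 3, and in the matching sentence of Section 8.2.1, make the sign specific to the endpoint: with c at or above zero, add c to the imputed active-arm values for ADAS-Cog, where higher is worse, and subtract c for ADCS-ADL, where lower is worse.

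State that the calibration offset C_prim follows the same convention. It is defined through the same imputation procedure and takes its sign from step 3, so saying so prevents the corrected and uncorrected conventions from being mixed.

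The cost is a sentence in each place and a sign in the analysis program. No data collection, sample size or trial conduct changes.
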